## **VI. Study Population**

### **Participant recruitment**

We plan to enroll a total of 27 healthy adults (all women), aged 21-50, into this study: 10 healthy women for the pilot stage and 17 women with a history of physical or sexual assault for the implementation stage. Given known sex differences in brain reactivity to stress and in neural correlates of PTSD (Felmingham, et al., 2010; Seo, et al., 2011), we focus on only women to maximize statistical power. In order to achieve these enrollment goals, up to 110 adults could be recruited and screened for eligibility. The participants would be recruited from local advertisements and flyers in public places. Additionally, we may recruit participants from previous or ongoing IRB-approved BIRC studies, provided they have consented to be recontacted for other studies by the study team.

Inclusion criteria for the healthy pilot stage participants will be no current Axis I psychological diagnoses, between the ages of 21-50, English speaking (due to lack of validated measures for non-English speaking populations), and medically healthy. Participants endorsing any of the following conditions will be excluded from the study: 1) current serious medical condition, 2) any internal metal objects, 3) under the age of 21 or over the age of 50, and 4) any current psychological disorder or psychiatric medication including acute suicidality or major depression. Any subjects that are at high risk or unstable (e.g. self-cutting, comorbid addiction) will also be excluded from the study.

Inclusion criteria for the implementation stage participants will be a history of physical or sexual assault, between the ages of 21-50, and medically healthy. Participants endorsing any of the following conditions will be excluded from the study: 1) current serious medical condition, 2) any internal metal objects, 3) under the age of 21 or over the age of 50, and 4) a psychotic disorder or developmental disorder including acute suicidality or major depression. Any subjects that are at high risk or unstable (e.g. self-cutting, comorbid addiction) will also be excluded from the study.

Due to safety concerns, participants with these conditions will be ineligible to participate:

- Claustrophobia, or the inability to lie still in a confined space
- Major medical disorders (e.g., HIV, cancer)
- Magnetic metallic implants (such as screws, pins, shrapnel remnants, aneurysm clips, artificial heart valves, inner ear (cochlear) implants, artificial joints, and vascular stents), as these may heat, pull, or twist in the strong magnetic field of the MRI scanner
- Electronic or magnetic implants, such as pacemakers, as these may stop working
- Permanent makeup or tattoos with metallic dyes
- A positive pregnancy test (for females), since the effect of strong magnetic fields on the developing fetus remains unknown and inconclusive. (We will conduct a pregnancy test for all female participants of childbearing potential on the day of the MRI scan.)
- A self-reported history of loss of consciousness (greater than 10 minutes)
- Physical disabilities that prohibit task performance (such as blindness or deafness)
- Psychotic disorders (e.g., schizophrenia)
- Any other condition that the investigator believes might put the participant at risk

Due to their effects on image quality, participants with the following MAY be ineligible to participate per Principal Investigator's judgment:

- Medications which may affect image quality (e.g., water pills)
- Nonremovable dental implants, such as braces or upper permanent retainers, as these will distort the MRI images we collect (note: fillings, crowns, and silver or gold teeth are OK)
- Any other condition, medication, or implant that the investigator believes would degrade image quality or render data unusable

## **VII. Investigational Plan**

### **Participant screening, consenting and assessments**

Participant assessment will occur in two parts. First, a phone screening will be conducted to ensure a high probability that participants are eligible for the study. This phone screening will assess self-report of whether the individual has a current mental health disorder, medical disorders, internal metal, claustrophobia, and transportation capability to UAMS. The phone-screening will be conducted by a trained research coordinator. If the participant meets probable inclusion criteria, the research coordinator will schedule the participant for part two of the assessment process.

Upon arrival to the BIRC for part two, the participant will first be given a written and verbal description of the study and informed consent. The PI or designated staff will discuss the informed consent form with the subject volunteer. The consent process will take place in a quiet and private room. Subjects may take as much time as needed to make a decision about their trial participation and may take the document home if desired. The person obtaining consent will thoroughly explain each element of the document and outline the risks and benefits, alternate treatment(s), and follow-up requirements of the study. Participation privacy will be maintained and questions regarding participation will be answered. No coercion or undue influence will be used in the consent process. No research related procedures will be performed prior to obtaining informed consent. All signatures and dates will be obtained. A copy of the signed consent will be given to the participant. The informed consent process will be documented in each subject's research record.

Following the obtainment of consent, part two will entail an in-person interview with a trained clinical research coordinator who will administer the BIRC Data Collection form, SCID, trauma assessment, questionnaires, and script generation forms. The research coordinator has a bachelor's level education in psychology and has received training in administering structured clinical interviews. A Clinical Research Nurse with over 20 years experience in structured clinical interviews will train the research coordinator on the SCID. The PI will supervise the research coordinator. Participants' trauma history will be assessed with an adapted version of the trauma assessment interview utilized in the National Women's Study (Resnick et al., 1993) and National Survey of Adolescents (Kilpatrick et al., 2000). Participants will additionally complete a battery of questionnaires, including the Posttraumatic Stress Disorder Checklist (PCL), Beck Depression Inventory (BDI), Childhood Trauma Questionnaire (CTQ), Positive and Negative Affect Scale (PANAS), and Difficulty in Emotion Regulation Scale (DERS). Mental health functioning will be assessed with the Structured Interview for DSM-IV Disorders (SCID-IV). This interview is expected to last approximately 3 hours. If the participant meets inclusion criteria for the study following the assessment, they will then be asked to complete the Stress/Trauma Script Generator Form . If the participant does not meet inclusion criteria following the assessment, they will not be allowed to be enrolled in the study, and they will be compensated and thanked for their time. For additional information on these forms, see Assessments section.

NOTE: Some participants from past BIRC studies or patients of the Women's Mental Health Program (WMHP) may have completed one or more of the clinical interviews used in the current project. If the participant has completed these interviews in the past, they may consent to use of these forms for the current project, provided the interviews were completed within the past year.

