## **IX. Risks and Benefits**

### **Potential risks**

*Internal metal during MRI scanning:* One potential safety concern is participant internal metal during MRI scanning, which can be painful and dangerous.

*Assessment of mental health and traumatic event exposure:* One potential psychological risk of the proposed study is the possibility that some participants might experience distress or become offended when asked questions pertaining to victimization and mental health history. Many people assume that asking such questions produces substantial distress, particularly in research settings. However, the empirical literature suggests that this risk is minimal, and that individuals with traumatic event histories actually report obtaining positive benefits from their participation in studies where traumatic event history is assessed (Griffin, Resick, Waldrop, & Mechanic, 2003; Newman, Walker, & Gefland, 1999).

*Assessment of suicidal ideation:* During the clinical interview (SCID) in the depression module, questions regarding suicidal ideation are asked. This may elicit distress from participants; however, there is a specific protocol should a participant report suicidal ideation, intent, or plan, and a protocol to decrease distress, described below. Individuals meeting criteria for current major depression will be excluded from the study, further decreasing the likelihood of reported suicidal ideation.

*Distress during the stress/trauma imagery task:* Another potential risk is that the script-guided imagery procedure will elicit anxiety/distress, in addition to the MRI environment itself. Participants are able to quit the task at any time by indicating to the MRI coordinator(s) that they wish to do so.

*Personal health information/Loss of confidentiality:* With all research participation, there is a risk that personal information obtained from research participants will be mishandled, and confidentiality may be compromised.

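### Clinical interviews up to a year old may be reused with no update, although eligibility depends on current psychiatric status

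*Combined protocol and SAP*

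**What the plan says.** The closing note of Section VII, Participant screening, consenting and assessments, concerns past participants of the centre's studies and patients of the women's mental health programme. Some of them "may have completed one or more of the clinical interviews used in the current project", and in that case "they may consent to use of these forms for the current project, provided the interviews were completed within the past year".

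The same section places the eligibility decision after the part-two assessment, which includes the SCID: "If the participant meets inclusion criteria for the study following the assessment, they will then be asked to complete the Stress/Trauma Script Generator Form".

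The criteria are in Section VI, Participant recruitment. The pilot stage requires "no current Axis I psychological diagnoses". The implementation stage excludes "a psychotic disorder or developmental disorder including acute suicidality or major depression". Both stages also exclude women judged high risk or unstable, with self-harm and addiction as examples. Section IX, Potential risks, makes the time frame of the depression criterion explicit: "Individuals meeting criteria for current major depression will be excluded from the study". It also says where suicidal thoughts are asked about: "During the clinical interview (SCID) in the depression module, questions regarding suicidal ideation are asked".

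**The concern.** A diagnostic interview describes a person's state when it was held. If one done up to twelve months earlier stands in for the Day 1 interview, a woman who has since become depressed or suicidal may be classed on her earlier state. She would then go into a scan that presents her own stress or trauma script four times (one model-building run and three neurofeedback runs), once with the instruction to increase arousal. Section V itself describes the assault sample as the more vulnerable one. What is at stake is the safety of enrolment and whether the eligibility criteria are applied as written.

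**Working it through.** The plan states no figure on this point, so the check sets the sections side by side.

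1. **Scope of the reuse rule (Section VII).** It covers any of the project's clinical interviews, with one year as the only limit. The SCID is not carved out, reuse is not confined to descriptive or historical data, and no items need updating.

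2. **Role of the SCID.** Section V, Assessments, describes it as the measure of current psychological functioning and drug use history. Section VII uses it to assess mental health functioning and decides eligibility after that assessment.

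3. **Time frame of the criteria.** Pilot: no current Axis I diagnosis. Both stages: acute suicidality, major depression (specified as current in Section IX), and high-risk or unstable state. All are about the present.

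4. **Combining 1 to 3.** With a reused SCID, the structured evidence on these criteria may be up to a year old, and the depression-module questions on suicidal ideation are not asked again.

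5. **Does another stated check before the scan fill the gap?**

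| Check | Section | What it settles |
|---|---|---|
| Telephone screen | VII | Self-report of a current mental health disorder. Suicidality is not listed. In the implementation stage a current disorder is not in itself an exclusion, so a positive answer does not decide eligibility. |
| Beck inventory | V, VII | Current severity of depression. It appears to be done afresh, because the note covers interviews only. No cut-off, review or action is stated. |
| High-risk or unstable exclusion; investigator discretion | VI | General judgement. No fresh assessment is named to inform it. |
| Procedure for actively suicidal participants | IX | Acts once such a participant is identified. It adds no new enquiry. |
| Scan-day screening | VI, VII | Metal, claustrophobia and pregnancy. |
| Psychologist's interview | VII | Emotional well-being, but after the scan. |

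None of these is a stated rule that decides current depression or suicidality again before exposure.

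6. **Size.** The expected number enrolled against the criteria would be

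N × (share with a reused interview) × (share whose status has changed) × (share missed by the other checks).

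The documents give N (10 pilot, 17 implementation) and none of the three shares, so the product cannot be evaluated.

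7. **Effect on the main analysis.** Section XII compares mean brain-state activation and SCR across the decrease, increase and decrease instructions within each participant. Diagnosis is not a variable in that comparison, and nothing in the documents shows that reuse would bias it.

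**The case against.** The best reply is that the note speaks only of using the forms for the project. It does not say that an old SCID alone decides eligibility. Part two is still an in-person visit with a trained coordinator under the principal investigator's supervision, and the checks in the table remain. The principal investigator attends each scan, and participants may stop at any time. All of this stands, and it lowers the chance that a change in status goes unnoticed. It does not remove the gap: the SCID feeds the eligibility decision, nothing is exempted, and no remaining check carries a rule for these criteria.

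A reader might infer four stronger things, which the documents do not support.

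- *That the suicide-risk safeguard does not operate for reused interviews.* Section IX mentions the SCID questions on suicidal ideation as a possible source of distress. The protective procedure, under Protections Against Risks, is not tied to the SCID or to Day 1. Reuse removes one structured point of detection; it weakens the safeguard without switching it off.
- *That a number of wrongly enrolled women can be given.* Assuming that 10% to 30% of the 17 reuse an interview and that 5% to 20% of those have a new episode gives 17 × 0.10 × 0.05 = 0.09 up to 17 × 0.30 × 0.20 = 1.02. Both rates are invented for illustration, and the sum assumes that the other checks detect nobody. It is not an estimate.
- *That the trial's conclusions are compromised.* Out-of-date diagnoses could blur the description of the sample, but no effect on the within-subject comparison is shown.
- *That a fixed list of SCID modules must be repeated in everyone.* Only items that decide a stage's criteria matter, and only where an interview is reused. PTSD, for example, is not an implementation-stage exclusion.

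**Conclusion.** The point holds as an inconsistency between the reuse rule and criteria on current status. Followed as written, the plan can leave eligibility resting on an assessment up to a year old, in both stages, before a procedure meant to provoke distress. This means that the route is open; it does not mean that such entry is likely. The conclusion rests on two readings of the text: that reused interviews serve the eligibility decision, because the SCID serves it and no exception is made, and that the questionnaires are completed anew. No size can be attached. The consequence is for screening and participant safety, with none shown for the planned comparison. It is worth correcting because the safety gain is specific and the change is small.

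**What to change.** Reconcile the note in Section VII with the criteria in Sections VI and IX:

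- limit reuse of earlier interviews to historical content, such as trauma history and past diagnoses;
- for anyone with a reused interview, require that the interview items deciding her stage's current-status criteria be completed afresh on Day 1, and base eligibility on those answers;
- leave the choice of items to the investigators, and name them in the protocol.

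The cost is a short addition to the text and some extra interview time for the reuse subset only. The coordinator already administers the SCID, so no new staff or instrument is needed.

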### **MRI**

Upon arrival to the BIRC for the fMRI scanning session, the participant will be given instructions for what they will be asked to do in the scanner. Prior to the scan, participants will complete the Strategies to Increase and Decrease Emotions form. Following the training, the participant will be screened for internal metal and claustrophobia. The participant will also be screened using the SAFESCAN® ferromagnetic detector per MRI Protocol and Procedures. The fMRI data will be acquired on a 3T Achieva X-series head-dedicated MRI scanner (Philips Healthcare, USA). The lead MRI coordinator has had extensive experience with high field imaging systems. Training on the current system was given to the coordinator by a Philips education specialist. A similar training was given to the back-up coordinator as well. Each MRI session will start with a localizer and reference scan to optimize head placement. Experimental tasks will be programmed with commonly used software (Presentation), and the images will be projected onto a translucent screen via a projector situated in an adjacent room. Anatomic fMRI scans will be acquired on all subjects for image alignment purposes.

**Assessing participant well-being:** The PI will be present at each scan. A clinical psychologist with significant PTSD experience will assess the participant's emotional well-being in person immediately following the scan with a private and informal clinical interview. Referral information about treatment options and contact information will be provided to participants who need it. Additionally, a trained research coordinator will contact the participants approximately one week later by phone to assess well-being. Referral information about treatment options and contact will be given to participants who need it. This research coordinator will have access to the clinical psychologist for questions regarding participants' clinical status.

### **Compensation**

Participants will be compensated for their time and participation. They will receive \$25 for the interview and \$25 for the fMRI scan. Participants will also receive \$15 for travel to scheduled appointments. Travel will be only compensated one time at the completion of the first visit. Participants driving themselves to UAMS for the study will have their parking validated. Bus tokens may also be provided to participants utilizing the Central Arkansas Transit (CAT) system.

## **VIII. Adverse Events: Adverse Events Reporting and Evaluation**

In adverse event reporting, all areas which mention the investigator refer to the PI and/or the PI's designee. All adverse events occurring during the course of the clinical study will be recorded on the Adverse Event Case Report Form. For all adverse events, the investigator must provide an assessment of the adverse event, its treatment and resolution, and its relationship to

the investigational drug or device. Special reporting procedures are required for certain adverse events.

### **Identification of Adverse Events**

An adverse event is defined as any new medical problem, or exacerbation of an existing problem, experienced by a subject while enrolled in the study, whether or not it is considered device-related by the investigator.

### **Serious Adverse Events**

Each adverse event will be assessed for its seriousness using the criteria outlined below. The term serious adverse event is not synonymous with a “severe” adverse event, which may be used to describe the intensity of an event experienced by the subject. An adverse event will be classified as serious if it meets any of the following criteria:

- Results in, or contributes to, a death
- Life-threatening (i.e., the subject was, in the opinion of the investigator, at risk of death at the time of the event, but it does not include an event that, had it occurred in a more severe form, might have caused death)
- Results in permanent disability or incapacity (i.e., permanent impairment of a body function or permanent damage to a body structure)
- Requires in-subject hospitalization or prolongs hospitalization
- Necessitates medical or surgical intervention to preclude a permanent disability or incapacity
- Results in a congenital anomaly or birth defect

Non-serious adverse events are all events that do not meet the criteria for a “serious” adverse event. If serious adverse event occurs, the investigator will promptly notify the reviewing IRB of such an event as soon as possible, but no later than ten (10) working days after first learning of the event.

### **Severity**

Each adverse event will be assessed for its severity, or the intensity of an event experienced by the subject, using the following:

1. **Mild:** Discomfort noticed, but no disruption to daily activity.
2. **Moderate:** Discomfort sufficient to reduce or affect normal daily activity.
3. **Severe:** Inability to work or perform normal daily activity.

### **Deaths**

The investigator will notify the sponsor and IRB as soon as possible, preferably within 24 hours but in no event later than 48 hours, of learning of subject’s death, regardless of whether the death is related or unrelated to the investigational drug and/or device. The investigator will attempt to determine, as conclusively as possible, whether the death is related to the device. The cause of death and the investigator’s discussion regarding whether or not the death was drug- or device-related will be described in a written report.

### **Pre-existing conditions**

Pre-existing conditions will not be reported as an adverse event unless there has been a substantial increase in the severity or frequency of the problem which has not been attributed to natural history.

### **Annual Reporting to IRB (Continuing Review)**

An annual report will be compiled and sent to the IRB to report on number of subjects enrolled in the study, safety events, and accrual schedule.

## **IX. Risks and Benefits**

### **Potential risks**

*Internal metal during MRI scanning:* One potential safety concern is participant internal metal during MRI scanning, which can be painful and dangerous.

*Assessment of mental health and traumatic event exposure:* One potential psychological risk of the proposed study is the possibility that some participants might experience distress or become offended when asked questions pertaining to victimization and mental health history. Many people assume that asking such questions produces substantial distress, particularly in research settings. However, the empirical literature suggests that this risk is minimal, and that individuals with traumatic event histories actually report obtaining positive benefits from their participation in studies where traumatic event history is assessed (Griffin, Resick, Waldrop, & Mechanic, 2003; Newman, Walker, & Gefland, 1999).

*Assessment of suicidal ideation:* During the clinical interview (SCID) in the depression module, questions regarding suicidal ideation are asked. This may elicit distress from participants; however, there is a specific protocol should a participant report suicidal ideation, intent, or plan, and a protocol to decrease distress, described below. Individuals meeting criteria for current major depression will be excluded from the study, further decreasing the likelihood of reported suicidal ideation.

*Distress during the stress/trauma imagery task:* Another potential risk is that the script-guided imagery procedure will elicit anxiety/distress, in addition to the MRI environment itself. Participants are able to quit the task at any time by indicating to the MRI coordinator(s) that they wish to do so.

*Personal health information/Loss of confidentiality:* With all research participation, there is a risk that personal information obtained from research participants will be mishandled, and confidentiality may be compromised.

